13.3 Vital Signs

The following vital signs measurements will be taken at the time points specified in the Schedule of Events (refer to the Protocol):

- Heart Rate (beats/min);
- Systolic blood pressure (SBP) (mmHg)
- Diastolic blood pressure (DBP) (mmHg)
- Respiratory rate (breaths/min)
- Temperature (°C)

All vital signs data collected at scheduled and unscheduled visits will be included in the listings, but only results collected as scheduled visits will be included in the summary tables.

The parameter names that will be used in the outputs will comprise of the test name and the unit of measure, for example, 'Systolic Blood Pressure (mmHg)'. Parameters will be sorted in the order that the measurements were collected in on the Vital Signs eCRF page within the tables and listings.

Vital signs measurements will present summary statistics for the results at the baseline and each scheduled post-baseline visit for each of the parameters. In addition, summaries will be presented for the change from baseline values at each scheduled post-baseline visit (continuous descriptive analysis).

In the summaries for each parameter one more decimal place will be added to the maximum number for the results reported in the eCRF for decimal precision. For example: 2 decimals reported in the eCRF will be reported as 3 decimals for precision.

In addition, parameters with clinically significant findings will be noted in the listings.

13.4 12-Lead Electrocardiogram (ECG)

The following ECG measurements will be taken at the time points specified in the Schedule of Events (refer to the Protocol):

- Heart Rate (beats/min)
- PR Interval (msec)
- RR Interval (msec)
- QT Interval (msec)
- QTc Interval (msec)
- QRS Duration (msec)
- Overall Investigator Finding

All ECG data collected at scheduled and unscheduled visits will be included in the listings, but only results collected as scheduled visits will be included in the summary tables.

The parameter names that will be used in the outputs will comprise of the test name and the unit of measure, for example, 'Ventricular Rate (beats/min)'. Parameters will be sorted in the order that the measurements were collected in on the ECG eCRF page within the tables and listings.

ECG measurements will present summary statistics for the results at the baseline and each scheduled post-baseline visit for each of the parameters. In addition, summaries will be presented for the change from baseline values at each scheduled post-baseline visit (continuous descriptive analysis).

The decimal precision for each parameter will be based on the maximum number of decimals to which the results were reported on the eCRF.

The summary of overall interpretation findings table will present counts and percentages for the reported results at baseline and each post-baseline visit/time point. Result categories will be ordered as 'Normal', 'Abnormal Not Clinically Significant (NCS)', 'Abnormal Clinically Significant (CS)' and 'Not Evaluable' (categorical descriptive analysis).

The listings of ECG measurements will include all the information collected data. In addition, the observations that are used as the baseline record (value) for each parameter will be flagged, and the change from baseline values at each post-baseline visit will be presented. For clinically significant assessments, cardiologist confirmation (Yes/No) and additional comments will be listed.

13.5 Pruritus Assessment

Pruritus will be assessed using a visual analog scale (VAS) and a 5-D (degree, duration direction, disability, and distribution) itch scale at each study visit after screening.

The 5-D Pruritus Scale is a multidimensional measure that quantifies pruritus. The scale consists of five domains: duration (1 item), degree (1 item), direction (1 item), disability (4 items), and distribution (16

locations of itch). All items of the first four domains were measured on a five-point Likert scale. A total score of 4 indicates 'no Pruritus' and 35 indicates 'most severe Pruritus'.

The scores of each of the five domains are achieved separately and then summed together to obtain a total 5-D score. 5-D scores can potentially range between 4 (no pruritus) and 35 (most severe pruritus.)

Single-item domain scores (duration, degree, and direction) are equal to the value indicated below the response choice (range 1-5). The score for the disability domain is achieved by taking the highest score on any of the four items. For the distribution domain, the number of affected body parts is tallied (potential sum 0-16) and the sum is sorted into five scoring bins:

- sum of 0-2 = 1
- sum of 3-5 = 2
- sum of 6-10 = 3
- sum of 11-13 = 4
- sum of 14-16 = 5.

The total score including change from baseline to each post baseline will be summarized. Domain and total scores along with changes from baseline will be listed.

In addition, the Pruritus visual analog scale result will be listed and summarized per time point by treatment group.

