### 5-D Pruritus Scale

**1. Duration:** During the last 2 weeks, how many hours a day have you been itching?

Less than 6hrs/day	6-12 hrs/day	12-18 hrs/day	18-23 hrs/day	All day
				
1	2	3	4	5

**2. Degree:** Please rate the intensity of your itching over the past 2 weeks

Not present	Mild	Moderate	Severe	Unbearable
				
1	2	3	4	5

**3. Direction:** Over the past 2 weeks has your itching gotten better or worse compared to the previous month?

Completely resolved	Much better, but still present	Little bit better, but still present	Unchanged	Getting worse
				
1	2	3	4	5

**4. Disability:** Rate the impact of your itching on the following activities over the last 2 weeks

	Never affects sleep	Occasionally delays falling asleep	Frequently delays falling asleep	Delays falling asleep and occasionally wakes me up at night	Delays falling asleep and frequently wakes me up at night
Sleep					
	1	2	3	4	5
	N/A	Never affects this activity	Rarely affects this activity	Occasionally affects this activity	Frequently affects this activity
Leisure/Social					
		1	2	3	4
Housework/Errands					
		1	2	3	4
Work/School					
		1	2	3	4

**5. Distribution:** Mark whether itching has been present in the following parts of your body over the last 2 weeks. If a body part is not listed, choose the one that is closest anatomically.

Head/Scalp	Present		Soles	Present
Face			Palms	
Chest			Tops of Hands/Fingers	
Abdomen			Forearms	
Back			Upper Arms	

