Source: Listing 16.2.9.2

[1] Baseline is defined as the last available, valid, non-missing observation prior to first study drug administration.
 N/A = Not Applicable. SD = Standard Deviation.

Table 14.3.5.2.2 Summary of 12-Lead ECG Interpretation (Safety Set)

Parameter: Overall ECG Interpretation

Visit	Category	Group 1 (N=XXX)	Group 2 (N=XXX)	Group 3 (N=XXX)
Baseline[1]	n	xx	xx	xx
	Normal	xx (xx.x%)	xx (xx.x%)	xx (xx.x%)
	Abnormal, Not Clinically Significant	xx (xx.x%)	xx (xx.x%)	xx (xx.x%)
	Abnormal, Clinically Significant	xx (xx.x%)	xx (xx.x%)	xx (xx.x%)
	Not Evaluable	xx (xx.x%)	xx (xx.x%)	xx (xx.x%)
Week xx	N	xx	xx	xx
	Normal	xx (xx.x%)	xx (xx.x%)	xx (xx.x%)
	Abnormal, Not Clinically Significant	xx (xx.x%)	xx (xx.x%)	xx (xx.x%)
	Abnormal, Clinically Significant	xx (xx.x%)	xx (xx.x%)	xx (xx.x%)
	Not Evaluable	xx (xx.x%)	xx (xx.x%)	xx (xx.x%)
Etc.	Etc.			

Source: Listing 16.2.9.2

[1] Baseline is defined as the last available, valid, non-missing observation prior to first study drug administration. Number of participants at each visit (n) will be used as the denominator for the calculation of all percentages.

Table 14.3.5.3 Summary of Pruritus Assessment - 5-D Pruritus Scale (Safety Set)

Visit Statistics	Group 1 (N=XXX)		etc.	Group x (N=XXX)		
	Actual Value	Change from Baseline		Actual Value	Change from Baseline	
Baseline [1]						
N	XX	N/A	XX	N/A	XX	N/A
Mean	XX	N/A	XX	N/A	XX	N/A
SD	XX	N/A	XX	N/A	XX	N/A
Median	XX	N/A	XX	N/A	XX	N/A
Minimum	XX	N/A	XX	N/A	XX	N/A
Maximum	XX	N/A	XX	N/A	XX	N/A
Week xx						
N	XX	XX	XX	XX	XX	XX
Mean	XX	XX	XX	XX	XX	XX
SD	XX	XX	XX	XX	XX	XX
Median	XX	XX	XX	XX	XX	XX
Minimum	XX	XX	XX	XX	XX	XX
Maximum	XX	XX	XX	XX	XX	XX

Source: Listing 16.2.9.7

[1] Baseline is defined as the last available, valid, non-missing observation prior to first study drug administration.
 N/A = Not Applicable. SD = Standard Deviation.

Table 14.3.5.4 Summary of Pruritus Assessment - Visual Analogue Scale (Safety Set)

Visit Statistics	Group 1 (N=XXX)		etc.	Group x (N=XXX)		
	Actual Value	Change from Baseline		Actual Value	Change from Baseline	
Baseline [1]						
N	XX	N/A	XX	N/A	XX	N/A
Mean	XX	N/A	XX	N/A	XX	N/A
SD	XX	N/A	XX	N/A	XX	N/A
Median	XX	N/A	XX	N/A	XX	N/A
Minimum	XX	N/A	XX	N/A	XX	N/A
Maximum	XX	N/A	XX	N/A	XX	N/A
Week xx						
N	XX	XX	XX	XX	XX	XX
Mean	XX	XX	XX	XX	XX	XX
SD	XX	XX	XX	XX	XX	XX
Median	XX	XX	XX	XX	XX	XX
Minimum	XX	XX	XX	XX	XX	XX
Maximum	XX	XX	XX	XX	XX	XX

Source: Listing 16.2.9.8

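### SAP 13.5 gives a 5-D pruritus range of 4 to 35 that its own scoring rules cannot produce (they give 5 to 25), and an itch-free patient can total either 5 or 8

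*SAP*

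**What the plan says.** SAP 13.5 gives the range of the 5-D total twice: "A total score of 4 indicates 'no Pruritus' and 35 indicates 'most severe Pruritus", and again "5-D scores can potentially range between 4 (no pruritus) and 35 (most severe pruritus").

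The same section fixes how the total is built:

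- "The scores of each of the five domains are achieved separately and then summed together to obtain a total 5-D score".
- Duration, degree and direction are one item each, and each takes the number printed under the chosen answer, from 1 to 5.
- For disability, which has four items, the rule is: "The score for the disability domain is achieved by taking the highest score on any of the four items".
- Distribution is a count of affected body parts (0 to 16) sorted into five bins scored 1 to 5. The lowest bin, 0 to 2 parts, scores 1.

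The programming note to Listing 16.2.9.7 repeats these domain rules without giving a range.

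On reporting, SAP 13.5 says "The total score including change from baseline to each post baseline will be summarized". Mock Table 14.3.5.3 shows that total and its change by treatment group. Domain scores are listed only.

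The questionnaire is in Protocol 19.2, Appendix B. Its direction item asks: "Over the past 2 weeks has your itching gotten better or worse compared to the previous month". The choices run from *Completely resolved* (1) to *Unchanged* (4) and *Getting worse* (5). None is meant for a patient who has had no itch. The SAP has no rule for that case.

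**The concern.** Two things do not fit.

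First, five domains with a minimum of 1 each cannot sum to 4, and five domains with a maximum of 5 each cannot sum to 35. A reader who takes the stated anchors at face value would see the worst attainable score as only about two thirds of the way up the scale.

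Second, absence of itch does not map to one score. The item is first completed on Day 1, and that visit supplies the baseline, so an arbitrary 3 points can enter the change score of an itch-free patient at either end of the comparison. Because direction is not summarised on its own, the table would not show where the change came from. Pruritus is the known class effect of this drug, so the output that describes it should be readable.

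**Working it through.** **Range.** Inputs are the domain rules in SAP 13.5 and the response values in Appendix B.

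| Domain | Lowest | Highest |
|---|---|---|
| Duration | 1 | 5 |
| Degree | 1 | 5 |
| Direction | 1 | 5 |
| Disability (highest item) | 1 | 5 |
| Distribution (binned) | 1 | 5 |
| Total | 5 | 25 |

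The sleep item alone spans 1 to 5, so disability reaches 5 whatever the top value of the three activity items. Enumerating every combination of answers gives 5 to 25, with neither 4 nor 35 among the totals.

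**Attempts to reproduce 4 to 35.**

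- Raw body-part count for distribution: 4 to 36.
- Distribution scored 0 when no part is affected: 4 to 25.
- Seven items summed, distribution dropped: 7 to 35.
- The same, with the three activity items at 0 when not applicable: 4 to 35.
- Seven items plus the distribution bin: 8 to 40, or 5 to 40 with not applicable as 0.

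Only the fourth matches. It contradicts both the five-domain sum and the highest-item rule, so it cannot be what the SAP intends to program.

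**Position of the worst score on the stated scale.** (25 − 4) / (35 − 4) = 21/31 = 68%, instead of 100%.

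**Itch-free total.** Order of terms: duration, degree, direction, disability, distribution.

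- Direction *Completely resolved*: 1 + 1 + 1 + 1 + 1 = 5.
- Direction *Unchanged*: 1 + 1 + 4 + 1 + 1 = 8.

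**Change scores that follow.**

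- Itch-free on Day 1 (8), itch that came and went, itch-free again (5): 5 − 8 = −3.
- Itch-free on Day 1 with *Completely resolved* (5), later itch-free with *Unchanged* (8): 8 − 5 = +3.
- Itch-free on Day 1 (8), new mild itch at two sites, now much better: 1 + 2 + 2 + 1 + 1 = 7, change −1 although itch is present.

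Three points is 3 / (25 − 5) = 15% of the attainable span.

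**Effect on an arm mean.** Let *a* be the share of an arm that goes from 8 to 5 between two itch-free visits, and *b* the share that goes from 5 to 8. The artefact in the mean is −3(*a* − *b*). The documents give neither share.

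As an illustration only, take *b* = 0, assume every affected patient ticked *Unchanged* on Day 1, and use the once-daily rates of 11% to 14% from study EYP001-103 (Protocol 1.4.3):

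- All itch resolved by that visit: −3 × 0.11 = −0.33 to −3 × 0.14 = −0.42.
- Half resolved: −0.17 to −0.21.

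The difference between arms also needs a placebo rate, which is assumed here. With 14% on EYP001a and all itch resolved in both arms:

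- Placebo 0%: −0.42.
- Placebo 5%: −3 × (0.14 − 0.05) = −0.27.
- Placebo 11%: −3 × (0.14 − 0.11) = −0.09.

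Equal rates give 0. These figures treat incidence over a whole study as the share resolved at one visit, so they are ceilings under the stated assumptions and not estimates.

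**The case against.** The strongest reply is that the wrong range does nothing. No derivation uses 4 or 35, the mock table prints no anchors, and correcting the text changes no reported number. That stands. It limits the consequence, but a SAP that states a scoring range its own rules exclude is still wrong as written.

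The second reply is that the direction problem belongs to the questionnaire and not to the SAP's arithmetic, and that recoding a patient's answer in the main score is a choice that needs support from the instrument's source, which cannot be checked here. That also stands, and it is why the main total should stay as marked.

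The third reply is that other outputs already describe itch. The visual analogue scale is summarised by arm, and its table is marked for both safety-committee reviews, while Table 14.3.5.3 is marked for neither. Adverse events are tabulated by preferred term and severity, 5-D domain scores are listed, and no formal inference is made on safety. This is correct and keeps the impact small.

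A reader might go further and infer that the artefact falls mainly on EYP001a and so understates the drug's pruritus burden, perhaps by about 2 points (3 × 0.67 = 2.0). The documents do not support that:

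- No placebo pruritus rate is given. The 15 of 24 in study EYP001-202 pools placebo with three active regimens (Protocol 5.4).
- The 67% comes from a twice-daily arm, and this trial doses once daily.
- The item compares with the previous month, so a patient long free of itch may return to *Unchanged*, which ends the artefact.
- Patients who are still itching usually raise the mean, and a false +3 is possible in either arm.

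What supports some concern is that Protocol 5.8.1 describes the itch as self-limited and says tolerance may develop. Itch that comes and goes is therefore plausible on active drug.

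**Conclusion.** The range error is certain: SAP 13.5 says 4 to 35, and its rules give 5 to 25. It affects how the score is read and no computed value.

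The direction gap is also real. An itch-free patient totals 5 or 8, so change from baseline can be off by up to 3 points in either direction. This rests on the response values printed in Appendix B and on the absence of a SAP rule for patients without itch. False improvement would be more frequent in whichever arm has more transient itch. Neither the arm nor the size of any difference can be settled from the documents.

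Overall this is a clear correction with limited consequences, confined to one descriptive safety table and its listing.

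**What to change.** 1. In both sentences of SAP 13.5, change the range to 5 (lowest possible score) to 25 (most severe). The label *no pruritus* should not be attached to the lower end, because an itch-free patient can also total 8.
2. Keep the main total as the sum of the domain scores from the marked answers.
3. Add to Table 14.3.5.3 a summary of the direction domain on its own.
4. Add a supplementary total, with its change from baseline, in which Direction is set to 1 at every visit, including Day 1, where Degree is *Not present*. List the raw answers unchanged.

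The cost is a few table rows and a footnote. The footnote should also say what is done when Degree is missing, or when it is *Not present* but body parts are ticked.

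The supplementary change will differ from the main one for patients who were itch-free on Day 1 and ticked *Unchanged*. For example, later mild itch at two sites, rated *Unchanged*, with no disability, totals 1 + 2 + 4 + 1 + 1 = 9. The main change is 9 − 8 = +1 and the supplementary change is 9 − 5 = +4. Showing both makes the artefact visible without redefining the planned score.

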13.6 Physical Examinations

By-participant data listings will be created for all complete physical examination and symptom directed assessments and all time points.

13.7 Liver Fibrosis and inflammation Assessment

The following Liver fibrosis and inflammation assessments will be taken at the time points specified in the Schedule of Events (refer to the protocol):

- ALT
- AST
- AST/ALT ratio
- High sensitivity C-reactive protein
- Interleukin 6
- Tumour necrosis factor alpha
- Procollagen type III N terminal peptide (Pro C3)
- Tissue inhibitor of metalloproteinases-1
- ELF score (HA, TIMP-2, PIIINP)

All liver fibrosis and inflammation data collected at scheduled and unscheduled visits will be included in the listings, but only results collected as scheduled visits will be included in the summary tables.

Liver fibrosis and inflammation assessments will present summary statistics for the results at the baseline and each scheduled post-baseline visit for each of the parameters. In addition, summaries will be presented for the change from baseline values at each scheduled post-baseline visit (continuous descriptive analysis).

13.7.1 Inferential Analyses

The following endpoint will be analyzed as described in sections 3.3:

- Liver Fibrosis and inflammation change from baseline from Day 1 to Week 16 of treatment

13.8 Liver Imaging

Liver imaging assessment will be listed for all time points.

The assessment of liver imaging table will present counts and percentages for the reported results at screening and Week 40 of follow up. Result categories will be ordered as 'Normal', 'Abnormal Not Clinically Significant (NCS)' and 'Abnormal Clinically Significant (CS)' (categorical descriptive analysis).

13.9 Pregnancy Test Results

All information related to pregnancy testing (urine and serum based) will be presented in the by-participant data listings.

14. IMMUNOGENICITY

No Immunogenicity analysis is planned for this study.

15. CHANGES TO THE PLANNED ANALYSIS

Safety review will be performed when 20 patients have reached w8 (expected by 1st March 2021 with data cut-off point defined to be 5th March 2021, replacing when 50% (n=25) patients reach week 8.

Sponsor decided on February 17th, 2021 to suspend further enrollments (after approx. 25 randomizations).

A request to deviate from the protocol has been initiated and executed by the sponsor and will be documented here. The changes to the planned analysis from the protocol are described in the following table:

Protocol	Key Changes
Based on the protocol section 11.3.3.1, for the primary efficacy endpoints (HBsAg decline), imputing missing data at 16 weeks as zero difference versus baseline	
 ▪ Missing primary efficacy data (HBsAg) will be imputed using multiple imputation process (MI SAS procedure) with MAR pattern.
Not in the protocol	
 ▪ Inferential Analyses for liver Fibrosis and inflammation change from baseline from Day 1 to Week 16 of treatment ▪ To summarize the Maximum CTCAE for ALT, AST, BILI and GGT for Post Treatment Assessments using CTCAE to do the toxicity grading.
Not in the protocol - The primary efficacy variables	
 ▪ Additional primary efficacy variable: 
 ▪ Anti-HBs ▪ Anti-HBe.
Based on the protocol section 11.3.3.1, for the primary efficacy endpoints (HBsAg decline), A Genotype [yes, no] needs to be included in the general linear model	
 ▪ A Genotype variable will be removed from the general linear model because the CRAs went back and cross checked there is no available historical genotype available in the medical history source other than what is currently in the EDC and also for most of the patients, there is no virus available in the samples to genotype.

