2. PROJECT OVERVIEW

2.1 Study Design

This is a prospective, multi-centre, international randomized, double-blind, placebo controlled, Phase 2a experimental study of oral FXR modulator EYP001a/placebo combined with Nucleos(t)ide analogues (NA) in virologically suppressed CHB patients to improve functional cure rates.

In total 49 eligible patients will be enrolled and randomized at approximately 14 study sites in 4 countries. Patients will be randomized prior to study drug (EYP001a or placebo and NA) administration on Day 1 in the ratio of 3:1 into 2 arms:

[figure not shown]
- Experimental Arm: EYP001a 200 mg once daily (QD) + NA daily (37 patients)
- Control Arm: Placebo + NA daily (12 patients)

Patients will also be stratified per HBeAg status, based on medical history HBeAg value or established during screening, to obtain a balanced randomization to both study arms.

The maximum total engagement duration for eligible patients in this study is up to 370 days: 90 days screening, 112 days (16 weeks) experimental treatment period and 168 days (24 weeks) follow-up on NA standard of care therapy (SOC) only.

Patients enrolled in the study will be assessed as outpatients. Patient screening will occur no more than 90 days prior to the Day 1 visit. Eligible patients will undergo further assessments on Day 1 to qualify for study drug administration on Day 1.

Figure 1: Study Design

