2.4 Sample Size

The primary endpoint is HBsAg reduction. Improvement of 1.0 on a log₁₀ scale at 16 weeks is considered to be clinically meaningful. The expected accrual rate is 2 to 4 patients per week but does not affect the sample size calculation. Note that the accrual rate will not affect sample size calculations. All assumptions are given in Table 1.

Table 1 Assumptions for primary endpoint	
Primary Endpoint	HBsAg reduction vs baseline on a log ₁₀ scale (“Chg”)
Null hypothesis	H0: Chg _{exp} – Chg _{ctrl} = 0
Alternative hypothesis	Ha: Chg _{exp} - Chg _{ctrl} = -1.0
SD of change vs baseline in experimental arm	1.08
SD of change vs baseline in control arm	1.08
Drop-out	10% over total study duration
Randomization ratio	3:1 for experimental:control (i.e. nE/nC=3)
Power	80%
Type I error rate (1-sided)	0.05

Chg: Change vs baseline; Ctrl: Control arm; Exp: Experimental arm; H0: Null Hypothesis; Ha: Alternative Hypothesis; SD: Standard Deviation

Patients who have dropped out, will be assumed to have a zero-difference vs baseline for conservativeness. To take this into account, the assumed effect of -1.0 on a log₁₀ scale, will be multiplied by 0.9, resulting in an assumed effect of -0.9. Using these assumptions, based on a test, 49 patients will need to be enrolled. Calculations are based on a t-test.

Note that the final analysis will be done, using a general linear model for repeated measures. Using this type of model, a better power is expected, thus sample size calculations can be considered conservative.

To calculate the power to detect a difference in HBsAg loss rate, we assumed a proportion of 0.5% in the placebo arm, and of 10% in the experimental arm. A trial including 49 patients results in a power of about 55% for this endpoint (using an un-pooled estimate of the variance), using a one-sided α of 0.05.

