3.7 Treatment Groups/Treatment Sequence

TFLs will be presented by treatment arms, and for all study patients in the given analysis set, where applicable.

The following order will be used for all summary outputs (with the treatment arm displayed, as applicable to the output):

- EYP001a 200 mg QD + NA daily (N=37)
- EYP001a 200 mg QD + NA daily HBeAg+ (N=xx)
- EYP001a 200 mg QD + NA daily HBeAg- (N=xx)
- Placebo + NA daily (N=12)
- Placebo HBeAg+ (N=xx)
- Placebo HBeAg- (N=xx)
- All HBeAg+ (N=xx)
- All HBeAg- (N=xx)
- All Study Patients (N=49)

The following treatment group labels will be used for all by-participant listings:

- EYP001a 200 mg QD + NA daily HBeAg+
- EYP001a 200 mg QD + NA daily HBeAg-
- Placebo HBeAg+
- Placebo HBeAg-

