16. INTERIM AND FINAL ANALYSIS

16.1 Interim Analysis (DSMC Review meeting)

An unscheduled DSMC review meeting of all available unblinded preliminary safety study data will be conducted when any stopping rules (Protocol Section 4.6) are met in two or more patients. All stopping rules will be listed by treatment group.

Two DSMC Review meeting are scheduled:

1. DSMC Safety Review Meeting on all available unblinded preliminary safety study data:
Safety assessment when 40.8% (n=20 out of 49) patients reach week 8 resulting in a decision on continuation of the study based on safety (Go/No go decision); enrolment would remain ongoing during this review.
2. DSMC Safety Review and Futility Analysis Meeting on all available unblinded preliminary virology, safety, PK and PD study data:
Safety and futility when 50% patients (n=25) reached week 12, resulting in a decision on continuation of the study (Go/No go decision) based on safety and evidence of a benefit of EYP001 (HBsAg, other secondary viral markers); enrolment is ongoing during this review.

The DSMC review meeting will be performed on all available primary and secondary endpoints according to the DSMC charter, which describes the overall guidelines, composition, roles, and responsibilities of the independent DSMC for the EYP001-201 study, including the selection of DSMC members, timing of meetings, methods of providing information to and from the DSMC, frequency and format of meetings, data analysis recommendations, and DSMC relationships with other parties participating in the conduct of this study.

The futility assessment will be performed to determine if EYP001 has no benefit at a point when 50% of patients have reached 12 weeks of dosing. The futility assessment will be performed by the DSMC according to the following rules:

- A treatment effect of -1.0 on a log₁₀ scale of HBsAg for the primary endpoint at 16 weeks, and a common standard deviation of 1.08 was assumed and the treatment effect would be -0.5 after 12 weeks of treatment, with common standard deviation of 0.7 Using a one-sided alpha of 0.05 and 80% power (beta = 0.20), a group sequential design, incorporating a futility and efficacy O'Brien-Fleming analysis when 50% of patients have reached 12 weeks of treatment, needs inclusion of 49 patients.
- Table 2 gives the probability of stopping early under the null and alternative hypothesis, at the time of the interim analysis.

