Based on the protocol clarification letter #13, the first interim analysis as described in the current EYP001-201 Study Protocol v3.0 dated 29th January 2020 corresponds to the first planned DSMC meeting and is performed on all available preliminary safety study data at the time of database snapshot (20 patients reach week 8, expected by 1st March 2021 with data cut-off point defined to be 5th March 2021.). Safety data only will be evaluated, based upon the review of the individual values (clinical significant abnormalities), descriptive statistics (summary tables, graphics) and if needed.). The term “first interim analysis” should be replaced by “DSMC Safety Review Meeting”. The “second interim analysis” corresponds to the second planned DSMC meeting covering safety review and futility analysis and is performed on all available virology, safety, PK and PD study data at the time of database snapshot when 25 patients have reached w12 (expected by 16th March 2021 with data cut-off point defined to be 15th May 2020). Safety and futility will be evaluated, based upon the review of the individual values (clinical significant abnormalities), descriptive statistics (summary tables, graphics) and on statistical analysis (futility analysis as described in section 11.5 of the study protocol). The term “second interim analysis” should be replaced by an interim analysis corresponding to “DSMC Safety and Futility Review Meeting”

There will be an additional database lock performed on all patient visits to Week 16 / Visit 9 for all randomised patients. All patients will be unblinded following database lock. Novotech Biostatistician will convert the datasets to CDISC format. Novotech data management will provide ENYO with raw data and Biostatistician will provide ENYO with CDISC converted datasets.

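### The SAP records enrolment suspended at about 25 patients, but its sample size, power, futility timing and Week 16 unblinding text were not brought into line

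*SAP*

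**What the plan says.** **Enrolment.** SAP 15 records the suspension: "Sponsor decided on February 17th, 2021 to suspend further enrollments (after approx. 25 randomizations". Its table of changes does not carry this through, and no sentence says whether enrolment may restart.

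**Size and power.** SAP 2.1 reads "In total 49 eligible patients will be enrolled and randomized at approximately 14 study sites in 4 countries". SAP 2.4 reads "Using these assumptions, based on a test, 49 patients will need to be enrolled", at 80% power, and defends the figure: "Using this type of model, a better power is expected, thus sample size calculations can be considered conservative". SAP 2.5 keeps 37:12, and 3.7 labels its total column "All Study Patients (N=49". SAP 16.1 bases the group sequential design on 49 patients and 80% power. The 80% therefore appears only in 2.4 and 16.1; the other sections carry only the numbers.

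**Reviews.** SAP 16.1 says of the safety review that "enrolment would remain ongoing during this review", and says the same in substance of the futility review. Section 15 dates the first: "Safety review will be performed when 20 patients have reached w8 (expected by 1st March 2021". Section 16.1 dates the second: "when 25 patients have reached w12 (expected by 16th March 2021 with data cut-off point defined to be 15th May 2020".

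**Week 16 unblinding.** SAP 16.1 adds a database lock once all randomised patients have reached Week 16, after which all patients are unblinded and datasets go to the sponsor. SAP 16.2 places unblinding after everyone has completed the study. Protocol 5.9 keeps site staff and patients blinded for the whole study, which runs to Week 40. SAP 6 has deviations reviewed before database lock without saying which lock, and SAP 4.1.6 requires the per-protocol (PP) set only before the final analysis.

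**The concern.** A SAP that records a suspension at about half the planned size and still gives 80% as its only power figure for the primary test leaves the reader with a number that may no longer apply. That matters most for a non-significant Week 16 result.

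The futility look is presented as a 50% look. If enrolment has ended it is a look at nearly the whole trial, and its printed data cut-off cannot be applied.

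Unblinding at Week 16 comes 24 weeks before the last efficacy visit, where HBsAg response and loss are still tested. The PP set supports the primary endpoint. As written, it could be settled by people who know the assignments.

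**Working it through.** **1. Reproduce the 49.** Inputs from SAP 2.4: one-sided alpha 0.05, SD 1.08 in both arms, 3:1 allocation, effect -1.0 × 0.9 = -0.9 for drop-out, t-test. Formula: df = n1 + n2 - 2; SE = 1.08 × √(1/n1 + 1/n2); ncp = d/SE; power = P(t' > t(0.95, df)) with t' non-central.

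- Exact 3:1 at N = 49: power 80.1%, the first N to reach 80%.
- Whole patients, 37:12: SE 0.359, ncp 2.51, power 79.6%.

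The plan's figure reproduces.

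**2. Same formula at about 25.** The SAP does not give the split; 19:6 is the whole-number split nearest 3:1.

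| Split | N | SE | Power for 0.9 | Power for 1.0 | Effect with 80% power |
|---|---|---|---|---|---|
| 37:12 | 49 | 0.359 | 79.6% | 86.5% | 0.91 |
| 19:6 | 25 | 0.506 | 53.3% | 60.8% | 1.30 |
| 20:5 | 25 | 0.540 | 48.9% | 56.0% | 1.38 |
| 18:7 | 25 | 0.481 | 56.8% | 64.5% | 1.23 |
| 17:5 | 22 | 0.549 | 47.5% | 54.5% | 1.42 |
| 21:7 | 28 | 0.471 | 58.5% | 66.3% | 1.20 |

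If the approximate 25 means 22 to 28 (my assumption), power for 0.9 is about 47-59% at splits close to 3:1. At 19:6 the shortfall against 37:12 is 79.6 - 53.3 = 26.3 percentage points. The detectable effect then exceeds the 1.0 log10 that SAP 2.4 treats as clinically meaningful.

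**3. What the repeated-measures model would have to recover.** At 19:6, 80% power for 0.9 needs an effective SD of 0.750. Variance reduction: 1 - (0.750/1.08)² = 52%. The SAP expects a gain but gives no figure.

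**4. Futility boundary at 25 patients.** Inputs from SAP 16.1: Week 12 effect -0.5, SD 0.7. With 18.75:6.25, SE = 0.7 × √(1/18.75 + 1/6.25) = 0.323. Normal approximation:

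- p at a difference of 0.085: Φ(0.085/0.323) = 0.604 (SAP 0.603).
- Futility under H0: 1 - 0.604 = 0.396 (SAP 0.4).
- Futility under Ha: 1 - Φ(0.585/0.323) = 0.035 (SAP 0.035).

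The boundary reproduces. What changes is the fraction: 25/49 = 51% of the planned patients, but nearly all of those enrolled if enrolment stays closed.

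**5. Dates.**

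- From 17 February 2021 to the expected review dates of 1 and 16 March 2021 is 12 and 27 days. Both reviews therefore fall within the suspension unless it had been lifted, and the SAP does not record that.
- From the cut-off of 15 May 2020 to the trigger of 16 March 2021 is 305 days, in the wrong order.
- Twenty-five patients at Week 12 by 16 March implies 25 at Week 8 by 16 March - 28 days = 16 February, or 22 February at the latest using the 3-day window at both visits. Yet only 20 are expected at Week 8 by 1 March.
- Put the other way: a 20th patient reaching Day 56 on 1 March was dosed on 5 January and reaches Day 84 on 29 March, after the date given for the 25th.
- A patient dosed on 17 February 2021 reaches Day 84 on 11 May 2021. A cut-off of 15 May 2021 would fit that, but the year is an inference, and changing it alone leaves the 16 March forecast unreconciled.

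**6. Unblinding.** Section 16.1 (after the Week 16 lock) and 16.2 (after study completion) give two times. Section 15 does not list the earlier one as a change. No text ties SAP 6 or 4.1.6 to the Week 16 lock.

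**The case against.** **Suspended is not terminated.** About 25 randomised is also the planned size of the futility look. If enrolment resumed, 49, 80% and 50% would all stand. This is right, so the power loss and the relabelling of the look are conditional. The wording on open enrolment is still inconsistent with Section 15 until the SAP says otherwise.

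**The arithmetic is sound.** A reader might infer that the sample size or the futility boundaries are miscalculated. They are not; steps 1 and 4 reproduce them. The boundaries are also non-binding.

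**Precision will be visible anyway.** SAP 3.3 reports least-squares mean differences with 95% intervals and standard errors, which show achieved precision directly. The suspension itself is disclosed. The -0.9 also reflects a zero-change assumption for drop-outs that Section 15 replaces with multiple imputation. These points soften the harm, but 80% remains the only power the SAP states for the primary test.

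**Some of this is inherited or minor.** Section 16.1 bases its account of the reviews on a clarification letter that the SAP's reference list dates to 27 January 2021, before the suspension, so the mismatch is probably a drafting lag (an inference). The mock tables already use N=xx, so 3.7 is only a label.

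**Blinding.** A reader might infer that sites and patients will be told their assignments, or that the PP set will be chosen with knowledge of treatment. The documents support neither. Protocol 5.9 still governs, 16.1 names only the sponsor as recipient of the datasets, deviation categories come from a plan dated January 2020, and SAP 4.1.6 adds an objective compliance rule. SAP 16.2 lists approval of the analysis populations ahead of unblinding, but for the final analysis, not the Week 16 lock. What stands is silence where a safeguard is cheap.

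**Conclusion.** The point holds as a failure to carry a recorded decision through the SAP. It should be fixed.

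Unconditionally: the enrolment wording in 16.1 conflicts with Section 15; the futility cut-off precedes its trigger by 305 days; the 16 March forecast conflicts with the Week 8 forecast; and the Week 16 unblinding is earlier than in 16.2, is not listed in Section 15, and has no stated access limit or link to the PP set.

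Conditionally, if enrolment does not resume: t-test power for -0.9 is about 53% at 19:6 (about 47-59% over 22 to 28 patients) instead of 80%, and the futility look covers nearly all patients. This rests on the SAP's own SD and t-test and on an assumed split near 3:1. The repeated-measures model may do better by an amount the SAP does not quantify.

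**What to change.** (a) State in Section 15 whether enrolment may resume. In 2.4 keep 49 as the original design. If enrolment stays closed, add the achieved number and its t-test power (roughly 50-60% at about 25 patients), noting that any gain from the repeated-measures model is unquantified. Use N=xx in 3.7.

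(b) In 16.1 make both enrolment statements consistent with the suspension. Describe the futility look as 50% of the planned patients and, if enrolment stays closed, essentially all enrolled patients. Correct the cut-off and reconcile the 1 March and 16 March 2021 forecasts with it.

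(c) In SAP 6 and 4.1.6 finalise important deviations and the PP set before the Week 16 unblinding. List that unblinding in Section 15, limit it to a named sponsor/CRO team, and state that sites and patients stay blinded to Week 40 under protocol 5.9.

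Cost: SAP wording, a less favourable power statement if enrolment stays closed, an earlier PP decision and an access list. No extra patients, visits or procedures.
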